13.0 CRITERIA FOR REMOVAL FROM STUDY

Patients may withdraw from the study at any time. They may also be discontinued from the study treatment and assessments at any time, at the discretion of the investigators. Specific reasons for discontinuing a subject from the study include:

- Patient inability or loss to follow-up
- Adverse events deemed significant by the investigators
- Protocol non-compliance
- Elective termination: A subject may withdraw consent at any point in the study
- Patient death

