10.0 EVALUATION DURING TREATMENT/INTERVENTION

Pre-treatment evaluations may be performed within 8 weeks of consent. After SRS, patients will be closely monitored for any evidence of toxicity, systemic illness or tumor progression. Acute toxicity assessment (see Appendix E) will occur by phone or clinic visit within 4 weeks (± 10 days) after the completion of radiotherapy. Follow-up clinic visits will take place 3 months, 6 months, 9 months, 12 months, 18 months and 24 months (± 8 weeks) after the completion of radiotherapy. At each follow-up visit, the investigators will complete the Spine Clinic Assessment form (see Appendix F). Spine MRI or CT will also be performed at the time of each follow-up, in accordance with routine standard of care.

Table 1: Pre-therapy and Follow-up Evaluations

Item	Pre-therapy (w within 8 weeks of consent)	Follow-up (3, 6, 9, 12, 18, 24 months \pm 8 weeks after the completion of SRS)
Inclusion/exclusion criteria	X	
CT myelogram or MRI perfusion	X	
Pathology diagnosis confirming metastatic disease	X	
Medical history	X	
Pregnancy test ¹	X	
Physical exam	X	X
Concomitant medications review	X	X
ECOG	X	X
Quality of Life assessments (MDASI and BPI) ²	X	X
Spine Clinic Assessment Form	X	X
MRI/CT scan ³	X	X
Adverse-event/toxicity assessment ⁴	X	X
Consent	X	

¹ For women of child-bearing potential, a urine or blood pregnancy test must be completed within 2 weeks prior to SRS.

- ² Patients will be asked to complete quality of life (MDASI and BPI) assessments at all timepoints, however this will remain optional. In instances where these questionnaires are not available in the participant's primary language, the participant will not be required to complete the questionnaire(s).
- ³ All patients are required to have MRI/CT based imaging at baseline and 3, 6, 9, 12, 18, and 24 months (\pm 8 weeks) after SRS. The imaging modality should remain constant for each patient throughout.
- ⁴ Only treatment-related adverse events will be reported. Acute toxicity assessment (see Appendix E) will occur by phone or clinic visit within 4 weeks (\pm 10 days) after the completion of radiotherapy.

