An intent-to-treat, stratified log rank test will be used to test whether or not the single-fraction SRS arm is inferior to the hypofractionated (3 fractions in total) SRS arm in terms of the local control rate. To set up a formal test we will use the 1-year local control rate as the surrogate of the efficacy (assuming that the two survival curves follow exponential distributions) and allow a 10% inferior margin. From a clinical standpoint, the investigators agreed that a difference of less than 10% is not regarded as significant. On this basis, we permit a 10% inferior margin. I.e., we will test $H_0: P_1 \leq (P_2 - 10\%)$ vs $H_1: P_1 > (P_2 - 10\%)$, where P_1 and P_2 denote the 1-year local control rate for the single-fraction arm and the 3-fraction arm, respectively. To approximately assess the power of the test, we estimate that the 3-fraction arm will yield a 1-year local control rate around 85% based on interim preliminary data from a multicenter Phase III trial (Protocol 10-154), and set the type I error (that is, declare single-fraction arm noninferior while it is not) rate at 0.10. When the two arms have equal efficacy, i.e., $P_1 = P_2 = 85\%$, the power (that is, declare the single-fraction arm noninferior while it is) of this noninferiority test⁴⁰ is 80% when there are 75 patients in each arm. Besides, since deaths without local failure are likely, competing risk analysis will also be used to estimate the local control rates of the two arms over time. We plan to enroll 150 patients within 2 years. If a

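### Section 13 lets investigators end assessments, not only treatment, for adverse events or non-compliance; this conflicts with the follow-up the intent-to-treat test needs and may censor the primary endpoint informatively

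*Combined protocol and SAP*

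**What the plan says.** Section 13.0 allows withdrawal by the patient and then adds: "They may also be discontinued from the study treatment and assessments at any time, at the discretion of the investigators". The listed reasons include "Adverse events deemed significant by the investigators" and "Protocol non-compliance". Both are separate from elective withdrawal of consent, loss to follow-up and death, which are also listed.

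Section 14.0 states the primary analysis: "An intent-to-treat, stratified log rank test will be used to test whether or not the single-fraction SRS arm is inferior" to the hypofractionated arm.

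Section 10.0 sets the schedule: "Follow-up clinic visits will take place 3 months, 6 months, 9 months, 12 months, 18 months and 24 months", counted from completion of radiotherapy. Footnote 3 to its Table 1 makes imaging at baseline and at these times a requirement for all patients. Section 1.0 lists the same time points but counts them from randomisation, with follow-up when possible or until death.

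Section 11.2 continues adverse event monitoring for 24 months after SRS or until death, and follows each event until it resolves or is judged permanent. Section 17.2 requires treatment-related toxicities and SAEs to be followed to resolution.

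Table 6 in Section 16.0.3 asks for outcome, toxicity and spine assessment forms when a patient goes off study. It schedules nothing after that.

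**The concern.** Ending assessments differs from ending treatment. Here treatment is over within 1 to 7 days (Section 1.0), so an investigator who uses this clause during follow-up stops only data collection, and the primary endpoint is read from that imaging. Section 12.0 measures response only up to the last follow-up visit, so a removed patient is in effect censored at removal.

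A log-rank test assumes that censored patients have the same later failure risk as those who remain. Removal for toxicity or for departing from the plan may break that assumption. It may also differ by arm. Section 15.2 has research staff and/or investigators told the assignment. Section 14.0 expects a possibly higher vertebral fracture risk with single-fraction treatment. Compliance with one visit may differ from compliance with three. Loss concentrated in the single-fraction arm could produce a false claim of non-inferiority. Loss elsewhere could hide a true one.

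**Working it through.** **1. The plan's own figure.** Inputs from Section 14.0: one-year local control of 85% in both arms, a 10-point margin, exponential curves, 150 patients over 2 years and 2 further years of follow-up. On error the plan says "set the type I error (that is, declare single-fraction arm noninferior while it is not) rate at 0.10". It states that power "is 80% when there are 75 patients in each arm".

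- Margin as a hazard ratio: ln(0.75)/ln(0.85) = 1.770.
- Hazard at 85%: −ln(0.85) = 0.1625 per year.
- Uniform accrual, 2 to 4 years of follow-up, no deaths or removals: event probability 0.383, so 150 × 0.383 = 57.5 events.
- Power = Φ(½√57.5 × ln 1.770 − 1.2816) = 0.81. Simulation of the non-inferiority log-rank test gives 0.804.

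The stated 80% is reproduced, but only with nobody removed. (It also ignores death and assumes follow-up beyond 24 months; those are separate matters.)

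**2. Uninformative removal.** No rate is given, so these are assumed. Removing 5, 10, 20 or 30% per year, ignoring death, leaves 53.5, 49.8, 42.8 or 36.6 events. The same formula gives power of 0.79, 0.77, 0.72 or 0.67.

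**3. Informative removal at the margin.** True one-year failure is 25% (single-fraction) and 15% (three-fraction). Assume a fraction c of an arm, with 50% one-year failure risk, is removed before failing. Then:

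- observed failure f = (p − 0.5c)/(1 − c), where p is the arm's true failure rate;
- observed HR = ln(1 − f₁)/ln(1 − f₂), with arm 1 the single-fraction arm;
- false non-inferiority = Φ(½√D × ln(1.770/HR) − 1.2816), with D events.

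D = 30 to 54 is also assumed. The upper end is just below the 57.5 above. The lower end is close to the 31.2 events expected under equal efficacy if the 16.5-month median survival at the top of the Section 3.1 range is treated as exponential censoring.

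| Removed, single-fraction / three-fraction | f₁ | f₂ | HR | False non-inferiority, D = 30 to 54 |
|---|---|---|---|---|
| 0 / 0 | 0.250 | 0.150 | 1.770 | 0.10 |
| 5% / 0 | 0.237 | 0.150 | 1.66 | 0.13 to 0.15 |
| 10% / 0 | 0.222 | 0.150 | 1.55 | 0.18 to 0.22 |
| 5% / 2.5% | 0.237 | 0.141 | 1.78 | 0.098 to 0.097 |
| 10% / 5% | 0.222 | 0.132 | 1.78 | 0.097 to 0.096 |
| 5% / 5% | 0.237 | 0.132 | 1.92 | 0.067 to 0.058 |
| 10% / 10% | 0.222 | 0.111 | 2.13 | 0.036 to 0.025 |

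**4. A different removal model.** In a simulation (75 per arm, 10,000 runs, unstratified test), a share of would-be progressors is censored before progression is recorded.

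| Share lost, single-fraction / three-fraction | Type I error | Power |
|---|---|---|
| 0 / 0 | 0.102 | 0.804 |
| 5% / 0 | 0.129 | 0.834 |
| 10% / 0 | 0.178 | 0.883 |
| 20% / 20% | 0.090 | 0.737 |
| 0 / 20% | 0.022 | 0.515 |

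Both models agree that the direction depends on which arm loses patients.

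**The case against.** The clause is permissive, so it may seldom be used. Other sections already point the other way: imaging is required of all patients, adverse events are monitored for 24 months, toxicities are followed to resolution, and status is recorded at removal. These points stand, but they show a conflict rather than a solution. Nothing says which rule prevails, and none of the safety provisions requires imaging after removal.

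Three stronger readings are tempting, and the documents do not support them.

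- A reader might infer that Section 13 makes an intent-to-treat analysis impossible. It does not: a removed patient can still be analysed in the assigned arm, censored at the last visit. What suffers is the follow-up that the analysis relies on.
- A reader might infer that lost failures always favour non-inferiority. That needs loss concentrated in the single-fraction arm. Nothing in the documents establishes such a pattern or the assumed 50% risk; if removed single-fraction patients had a 10% risk, the same formula gives 0.06 to 0.08. The fracture link is also limited, since Section 17.2 describes fracture as seldom a significant adverse event.
- A reader might infer that randomised patients who never receive SRS have no schedule. Section 1.0 gives one from randomisation. The fault is that it disagrees with Section 10.0.

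**Conclusion.** The point holds as a conflict in the protocol that should be corrected. Section 13 lets investigators who know the arm end endpoint imaging for reasons that may relate to outcome and to treatment. This cannot be squared with the imaging and adverse event follow-up required elsewhere, and it weakens the intent-to-treat comparison.

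The size and direction of any bias are unknown. Under the assumed 5% or 10% removal and 50% failure risk, false non-inferiority ranges from about 0.03 (equal loss in both arms) to 0.22 (loss in the single-fraction arm only), against a nominal 0.10. A 2:1 split leaves it nearly unchanged. These figures show sensitivity and are not forecasts. That removal costs events, and that the stated 80% power has no allowance for it, does not depend on the 50% risk or on how the loss falls between arms.

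**What to change.** - In Section 13, define leaving protocol treatment separately from leaving the study. State that adverse events and non-compliance do not end the scheduled standard-of-care imaging or outcome data collection.
- State that follow-up ends only at death, withdrawal of consent to follow-up, loss to follow-up, or 24 months.
- Record the reason for every removal and tabulate it by arm. Say in Section 14 how patients who do leave are censored.
- Reconcile Section 1.0 (visits counted from randomisation) with Section 10.0 (from completion of SRS), so that randomised patients who receive no SRS have a defined schedule.
- Reconcile Section 13 with the toxicity follow-up in Sections 11.2 and 17.2.

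The cost is protocol wording and a few extra data entries. Section 10.0 describes the follow-up scans as routine care, so no added imaging burden is expected.

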14.0 BIOSTATISTICS

The primary endpoint of this multicenter Phase III noninferiority study is the local tumor control after post-operative spinal stereotactic radiosurgery (SRS). A noninferiority study design is justified on the basis that both treatment options have their advantages and disadvantages with currently mixed data about the relative tumor control offered by hypofractionated and single-fraction SRS. Some data suggest that single-fraction SRS may offer superior local control and since only one treatment visit is required it is cheaper and more convenient for patients. On the other hand, data suggest that single-fraction treatment may be associated with a higher risk of vertebral body fractures, which is considered a treatment-related toxicity. Determining whether single-fraction SRS and hypofractionated SRS offer comparable local tumor control will allow physicians to make treatment decisions based on factors such as cost and toxicity risk.

Lack of local radiographic progression will be defined as local tumor control. Patients will be randomized in a 1:1 fashion and the local control in the two treatment arms (single-fraction SRS vs. hypofractionated SRS) will be assessed. The patients will be stratified according to participating center (MSK, MGH, JHH, Stanford), presence or absence of prior radiation history at the study level, and radioresistance of the primary tumor histology, with breast and prostate classified as radiosensitive and the remaining solid tumor metastases (i.e. melanoma, sarcoma, thyroid, renal, colorectal) classified as radioresistant.

An intent-to-treat, stratified log rank test will be used to test whether or not the single-fraction SRS arm is inferior to the hypofractionated (3 fractions in total) SRS arm in terms of the local control rate. To set up a formal test we will use the 1-year local control rate as the surrogate of the efficacy (assuming that the two survival curves follow exponential distributions) and allow a 10% inferior margin. From a clinical standpoint, the investigators agreed that a difference of less than 10% is not regarded as significant. On this basis, we permit a 10% inferior margin. I.e., we will test $H_0: P_1 \leq (P_2 - 10\%)$ vs $H_1: P_1 > (P_2 - 10\%)$, where P_1 and P_2 denote the 1-year local control rate for the single-fraction arm and the 3-fraction arm, respectively. To approximately assess the power of the test, we estimate that the 3-fraction arm will yield a 1-year local control rate around 85% based on interim preliminary data from a multicenter Phase III trial (Protocol 10-154), and set the type I error (that is, declare single-fraction arm noninferior while it is not) rate at 0.10. When the two arms have equal efficacy, i.e., $P_1 = P_2 = 85\%$, the power (that is, declare the single-fraction arm noninferior while it is) of this noninferiority test⁴⁰ is 80% when there are 75 patients in each arm. Besides, since deaths without local failure are likely, competing risk analysis will also be used to estimate the local control rates of the two arms over time. We plan to enroll 150 patients within 2 years. If a

patient has multiple eligible lesions, all of them will be treated within the randomized arm and each eligible lesion (non-contiguous lesions treated with a separate radiation contour) will be treated as a separate study unit. After the enrollment of the final patient, a 2-year follow up is planned. Three interim analyses are planned and will be conducted at the time of the DSMB annual review of the study. The O'Brien-Flemming boundary will be applied for assessing statistical significance. Specifically, the rejection regions in terms of the corresponding Z-scores are $Z > 3.09$, $Z > 2.06$, $Z > 1.63$ and $Z > 1.39$ for the three interim looks and the final look, respectively. We expect that very few patients will have multiple lesions and thus we do not plan to examine the correlation among multiple lesions from the same patients. Instead, the analysis of the primary endpoint will be conducted at lesion level as mentioned above. Data will be collected from all four centers and analyzed at MSKCC.

In consideration of the fact that a large cohort will be recruited, this study will be continuously monitored to protect patients from excess toxicity. For each arm, we anticipate that the true rate of any grade 4 toxicity within 24 months post SRS is less than 10%. All grade 4 toxicities or greater observed will be reviewed by the study chair. Moreover, using a stopping rule based on sequential probability ratio test (SPRT), each arm of the study is monitored for any grade 4 or above toxicities that are judged to be associated with the radiation treatment. This stopping rule specifies that for each arm, the study will be halted if any of the following conditions occur: >4 /first 15; >6 /first 35; >9 /first 55; or if more than 12 unacceptable toxicities are observed within 24 months post SRS when the last (75th) patient has completed the trial. When the true toxicity rate is 10%, this stopping rule has a probability of 0.1 to stop the trial. When the true toxicity rate is 20%, this stopping rule has a probability of 0.8 to stop the trial. For this stopping rule we will use each patient as a study unit.

Toxicity outcomes and patterns of complications are summarized and tabulated in Section 11.0. Comparisons will be made using Wilcoxon rank sum tests and proportion tests. QOL results measured by MDASI scores and pain control results measured by BPI scores will also be summarized and compared between the two arms by Wilcoxon rank sum tests. As multiple measurements will be taken and thus multiple tests will be conducted, test p-values will be adjusted by the false discovery rate method.

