4.0 OVERVIEW OF STUDY DESIGN/INTERVENTION

4.1 Design

This is a therapeutic Phase III prospective randomized non-inferiority study investigating the efficacy and safety of post-operative single-fraction or high-dose hypofractionated SRS. Diagnostic and eligibility decisions for patients entering the study will involve the RSA and ultimately will be made by the consenting professionals.

Eligible patients will have undergone surgery for spinal decompression and stabilization in order to treat spinal metastases and demonstrate adequate separation between tumor and the spinal cord on post-operative CT myelogram or MRI perfusion. Contrast used for the CT myelogram will not affect renal function and will be performed regardless of the participant's renal function. The CT myelogram or MRI perfusion will be performed at all participating sites. CT myelogram will be used for treatment planning, since spinal instrumentation generates artifact in MR imaging which may complicate spinal cord contouring. For instances in which the CT myelogram cannot be tolerated by the patient, MRI with perfusion will be an acceptable alternative for treatment planning. However, post-operative MR imaging provides adequate resolution in order to reliably diagnose tumor recurrence and will be used to monitor patients for recurrence, unless patients are unable to undergo MR imaging.

Patients who are candidates for either single-fraction or high-dose hypofractionated SRS will be recruited into the study and randomized in a 1:1 fashion to one of the two treatment arms. An Acute Toxicity Assessment (see Appendix E) will be performed via phone or clinic visit within 4 weeks (\pm 10 days) after the completion of SRS. Patients will have the option to complete the MD Anderson Symptom Inventory – Spine Tumor Module (MDASI) and the Brief Pain Inventory (BPI) at the time of recruitment and at 3, 6, 9, 12, 18 and 24 months (\pm 8 weeks) after their treatment during follow-up care. At these same time points, the study investigators will complete the Spine Clinic Assessment form (see Appendix F). Follow-up MRI imaging will also be obtained at the same time points, including axial and sagittal T1, T2, STIR and gadolinium-enhanced T1 sequences. For those patients that are not candidates for

MRI, CT imaging will be performed. Patients will be monitored for development of radiation- and surgery-related toxicity or complications. Imaging will be reviewed for evidence of local tumor progression.

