7.0 RECRUITMENT PLAN

Due note is taken of the NIH policy of inclusion of women and minorities in research protocols. Patients will not be excluded from the protocol based on gender, race or age. The study population will be representative of the range of patients undergoing post-operative SRS at the participating sites.

Potential subjects will be identified by a member of the patient's treatment team, the research team and/or the protocol investigators at MSKCC, MGH, JHU, or Stanford. All subjects for this study will be recruited from a pool of patients of the investigators. Subjects who appear to be eligible will be presented with the opportunity to participate. The study will be posted on the clinicaltrials.gov website. Furthermore, the trial will be posted on the MSKCC website under clinical trials.

Patients will be approached and consented anytime between the pre-operative discussion about surgery and the start of SRS treatment planning. Once the post-operative CT myelogram or MRI perfusion demonstrates separation of tumor and the spinal cord and all of the inclusion criteria are met, the patient will be randomized before the start of radiation treatment planning to receive either single-fraction or hypofractionated SRS within 8 weeks of surgery. The recruiting physicians will be familiar with the patient's medical history and health status at the time of recruitment since they will be directly involved in the post-operative radiation planning and will not require a waiver of authorization. Screening for the eligibility will not require collection of any additional patient information since all of the information required to determine patient eligibility will be required in order to appropriately plan the post-operative SRS.

Patients will not be recruited outside of the post-operative treatment pathway and no advertisement or patient compensation will take place.

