9.0 TREATMENT/INTERVENTION PLAN

Patients will undergo SRS treatment simulation in supine position following a CT myelogram or MRI perfusion. They will be immobilized in the custom-fitted cradle which will be used for the duration of their treatment. A thermoplastic mould mask will be used for lesions above T4. Target volume contouring will be done according to the guidelines proposed by the International Spine Radiosurgery Consortium³⁸. The gross tumor volume (GTV) will be contoured according to standard institutional practice to include the entire tumor visible on any of the pre- or post-operative imaging studies, including MRI and CT. Every attempt will be made to include the entire preoperative tumor volume into the GTV even if a part or all of it were resected during surgery. The clinical tumor volume (CTV) will be expanded to include all of the adjoining marrow spaces in the vertebral body as defined by Cox et al³⁸. The planned treatment volume (PTV) will be expanded 2-3 mm around the CTV, but will not include the spinal cord. The spinal cord as defined on the CT myelogram or MRI perfusion will be excluded from all treatment contours. Inverse treatment planning will be carried out with the goal of maximizing the percentage of PTV receiving the 100% of the planned dose with a requirement of PTV V100 \geq 80%. GTV Dmin >15 Gy will be required with a goal V100 > 90%. The prescribed dose will be normalized to the 100% isodose line or its equivalent, depending upon institutional practices. In order to account for variability of delivery systems, doses will be prescribed that are equivalent to the absolute dose stipulated in the protocol. Volumetric modulated arc therapy (VMAT) may potentially be utilized. In order to ensure homogeneity of treatment plans among institutions, the first three treatment volumes from each institution will be reviewed by representatives from each institution and differences in contouring will be discussed in order to arrive at consensus.

Treatment will be administered using 6- and/or 15-MV photons using 7-9 coplanar beams with dynamic multi-leaf collimation. At the time of treatment, a three-dimensional kilovoltage cone-beam CT image obtained once the patient is positioned will be used to match the vertebral anatomy to the simulation scan and immediately before treatment patient alignment will be checked using two-dimensional kilovoltage verification. In case of 2mm or larger deviation, patient will be repositioned.

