The organ at risk tolerances will be different for the two treatment arms and are presented in Appendix G (Single-Fraction) and Appendix H (Hypofractionated). The single-fraction treatment will be administered in one day while the hypofractionated treatment will be administered every other day. Total treatment time per fraction including set up will be 60-75 minutes per fraction.

Nausea, dysphagia and diarrhea will be treated according to standard institutional practice.

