16.3.2 Additional IRB Correspondence

Continuing Review Approval

The Continuing Review Approval letter from the participating site's IRB and the most current approved version of the informed consent form should be submitted to MSKCC within 7 days of expiration. Failure to submit the re-approval in the stated timeline will result in suspension of study activities.

Deviations and Violations

A protocol deviation on this study is defined as a request to treat a research participant who does not meet all the eligibility criteria, pretreatment evaluation, or who requires alteration in their study plan. If a deviation from this protocol is proposed for a potential or existing

participant at MSKCC or a participating site, approval from the MSKCC IRB/PB is required prior to the action. Participating sites should contact the MSKCC PI who will in turn seek approval from the MSKCC IRB/PB.

A protocol violation is anything that occurs with a participant, which deviated from the protocol without prior approval from the MSKCC IRB/PB. For protocol violations that are identified after they occur, the participating site should report to MSKCC as soon as possible. The MSKCC PI will in turn report the violation to the MSKCC IRB/PB.

Participating sites should report deviations and violations to their institution's IRBs as soon as possible per that site's institutional guidelines. Approvals/acknowledgments from the participating site IRB for protocol deviations and violations should be submitted to MSKCC as received.

Other correspondence

Participating sites should submit other correspondence to their institution's IRB according to local guidelines, and submit copies of that correspondence to MSKCC.

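### The non-inferiority claim rests on intent-to-treat alone, although patients are randomised before planning shows whether the assigned schedule can be delivered; a supportive per-protocol analysis should be prespecified

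*Combined protocol and SAP*

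**What the plan says.** - **Analysis set.** Section 14.0 (Biostatistics): "An intent-to-treat, stratified log rank test will be used to test whether or not the single-fraction SRS arm is inferior". The competing-risk analysis added there changes the estimator. It does not change who is analysed or under which treatment.
- **Timing.** Section 7.0 (Recruitment Plan): "the patient will be randomized before the start of radiation treatment planning to receive either single-fraction or hypofractionated SRS within 8 weeks of surgery".
- **Planning after randomisation.** Section 9.0: "Inverse treatment planning will be carried out with the goal of maximizing the percentage of PTV receiving the 100% of the planned dose", with minimum coverage of PTV V100 ≥ 80% and GTV Dmin > 15 Gy. The same section adds: "The organ at risk tolerances will be different for the two treatment arms". The tolerance values are in Appendices G and H, of which only the titles are available here.
- **Safeguards.** Section 4.1: "Patients who are candidates for either single-fraction or high-dose hypofractionated SRS will be recruited into the study". Section 6.2 excludes patients with less than 2 mm between tumour and cord. Section 16.3.2 counts a participant "who requires alteration in their study plan" as a deviation that needs approval from the MSKCC IRB/PB beforehand.
- **Removal.** Section 13.0 lists "Protocol non-compliance" among the reasons for discontinuing a subject, and discontinuation can cover assessments as well as treatment.

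No section says how a patient whose assigned plan cannot meet the limits is recorded or analysed.

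**The concern.** In a superiority trial, patients who receive the other arm's treatment pull the result toward no difference, which makes intent-to-treat cautious. In a non-inferiority trial the same pull favours the claim. Here the step that shows whether a schedule is deliverable comes after allocation, and at least some of its limits depend on the arm. The short treatment course does not help, because the problem arises before the first fraction. If intent-to-treat alone shows non-inferiority, a reader cannot tell comparable local control from dilution. The design already accepts a type I error of 0.10 and a 10-point margin, so there is little room for further inflation. In addition, a patient discontinued for non-compliance could lose the follow-up imaging that intent-to-treat itself depends on.

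**Working it through.** **Inputs (Section 14.0).** 3-fraction 1-year control 85%; margin 10 points, so 75% at the margin; exponential curves; type I error 0.10, one-sided (z = 1.2816); 75 patients per arm; accrual over 2 years, then 2 years of follow-up.

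**Step 1: the plan's own power.**
- Hazards: −ln 0.85 = 0.1625 and −ln 0.75 = 0.2877. Margin hazard ratio: 0.2877 / 0.1625 = 1.770, ln = 0.571.
- Probability of an observed failure with hazard λ: 1 − [exp(−2λ) − exp(−4λ)] / (2λ). This is 0.383 at 85% control and 0.572 at 75%, ignoring deaths.
- Events when both arms are at 85%: 150 × 0.383 = 57.5.
- Power: Φ(√(57.5/4) × 0.571 − 1.2816) = Φ(0.883) = 81.1%; simulation gives 80.8%. The stated 80% reproduces.

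**Step 2: dilution at the margin.** Suppose the true rates are 75% and 85%, and a fraction c of the single-fraction arm receives the 3-fraction schedule and attains 85%.
- Apparent single-fraction rate: P1 = 0.75(1 − c) + 0.85c.
- Apparent hazard ratio: h = ln P1 / ln 0.85.
- Type I error: Φ(√(D/4) × ln(1.770/h) − 1.2816), where D is the number of events.

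The documents give no event count. Without deaths, the count at the margin is 75 × (0.572 + 0.383) ≈ 72. I take 33 as an assumed low value, because Section 14.0 expects deaths without local failure.

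| c (assumed) | P1 | h | D = 33 | D = 57.5 | D = 72 | Simulation, no deaths |
|---|---|---|---|---|---|---|
| 0% | 0.750 | 1.770 | 0.100 | 0.100 | 0.100 | 0.101 |
| 5% | 0.755 | 1.729 | 0.112 | 0.116 | 0.119 | 0.123 |
| 10% | 0.760 | 1.689 | 0.126 | 0.135 | 0.140 | 0.142 |
| 20% | 0.770 | 1.608 | 0.157 | 0.179 | 0.191 | 0.200 |

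Example, c = 10%, D = 72: ln(1.770/1.689) = 0.0471; √18 = 4.243; 4.243 × 0.0471 − 1.2816 = −1.082; Φ = 0.140.

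**Step 3: power of a per-protocol analysis when the arms are equal at 85%.** Excluding 10% of the single-fraction arm leaves 67.5 + 75 = 142.5 patients and 142.5 × 0.383 = 54.6 events, with allocation 0.474 : 0.526. Power = Φ(√(54.6 × 0.474 × 0.526) × 0.571 − 1.2816) = 79.5%. With 20% excluded it is 77.6%.

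**Step 4: can per-protocol mislead?** Assume that 10% of patients have undeliverable single-fraction plans, that their control is 20 points worse on either schedule, and that the arms' overall true rates are 75% and 85%.
- Deliverable single-fraction patients: 0.75 + 0.10 × 0.20 = 0.77.
- On the 3-fraction schedule, the deliverable group is at 0.87, so the switched patients are at 0.87 − 0.20 = 0.67.
- Intent-to-treat sees 0.9 × 0.77 + 0.1 × 0.67 = 0.76 against 0.85: type I error 0.135 (57.5 events).
- Per-protocol sees 0.77 against 0.85: 0.177 (about 54.6 events).

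With a 10-point gap instead, the two are about equal (0.135 and 0.134).

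These calculations ignore the interim looks, stratification and correlation between lesions in one patient.

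**The case against.** **A documented one-way flow?** A reader might infer that the protocol sends failed single-fraction plans to the 3-fraction arm. It does not say so. The tolerance values cannot be seen, and the coverage minima are stated without distinguishing the arms. Nothing readable shows that single-fraction plans fail more often. An undeliverable plan could also end in no study treatment or in removal from the study, which is a missing-data problem and could bias either way. This objection stands.

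**Safeguards.** Recruitment is limited to candidates for either schedule, cord separation is shown before randomisation, the recruiting physicians take part in planning, and altered plans need prior approval. These make a rate near 5% at least as plausible as 10–20%. They do not remove the risk: candidacy is judged before dosimetry, and approval of a deviation does not settle how the patient is analysed.

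**The model.** Switched patients are given the comparator's average control, but patients with difficult plans are a selected group and may not attain it. The figures in Step 2 are illustrations, not predictions.

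**The remedy.** Step 4 shows that a per-protocol analysis can be the more lenient of the two. It is therefore tempting, but not justified, to make per-protocol success a formal condition of the claim or to treat it as the truer answer. A set chosen after randomisation can only support the primary analysis.

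**Conclusion.** The gap is real and modest. Intent-to-treat is the only analysis set behind a non-inferiority claim, the design leaves room for the assigned schedule not to be delivered, and nothing planned would show whether that affected the result. Under the assumed one-way crossover of 5%, 10% and 20%, type I error rises from 0.10 to about 0.11–0.12, 0.13–0.14 and 0.16–0.19 over 33 to 72 events; simulation without deaths runs slightly higher. These sizes rest on an assumed rate, an assumed direction, and switched patients doing as well as the comparator arm on average. A reader might go further and conclude that the trial's error rate is inflated as designed. The documents do not support that: they report no crossover rate and no direction. What they support is a cheap improvement, namely a prespecified supportive analysis and transparent reporting of treatment received.

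**What to change.** In Section 14.0:

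1. Keep intent-to-treat as the primary analysis. State that patients who do not receive the assigned schedule stay in imaging follow-up, and align Section 13.0 with this.
2. Prespecify a supportive per-protocol analysis of eligible patients who received the full assigned regimen, with the same stratified test, 10% margin and one-sided alpha of 0.10.
3. Report the confidence bound from each analysis against the margin. If intent-to-treat meets the margin but the per-protocol bound crosses it, describe the non-inferiority claim as not robust.
4. Report crossover and non-delivery by arm, with reasons, from the External Beam Radiation form already required in Table 6 (Section 16.0.3).

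The cost is one extra analysis, largely on data already collected, plus continued imaging for patients who might otherwise be taken off study. Power in the per-protocol set falls slightly, from 81.1% to 79.5% if 10% of the single-fraction arm is excluded and to 77.6% if 20% is. The main downside is that this set is selected after randomisation and can itself be biased, so it should be read beside intent-to-treat and not in its place.
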